### 2.5.2 Statistical hypothesis, model, and method of analysis

The primary efficacy endpoint will be analyzed using an Analysis of Covariance (ANCOVA) model, in which the response variable will be the percentage change from baseline at Day 150 in LDL-C, treatment will be included as fixed-effect factor and baseline LDL-C will be included as a covariate.

The primary statistical hypothesis is stated as below.

- $H_0$ : the mean difference (inclisiran minus placebo) in percentage change from baseline at Day 150 in LDL-C is no less than zero.
- $H_1$ : the mean difference (inclisiran minus placebo) in percentage change from baseline at Day 150 in LDL-C is less than zero.

The study can be claimed a success if the null hypothesis ( $H_0$ ) is rejected at the one-sided significance level of 0.025.

The statistical test will be performed at the one-sided significance level of 0.025 based on the ANCOVA model. The estimate and the 95% confidence interval will be provided for the adjusted mean difference between inclisiran and placebo, and for the adjusted mean for both inclisiran and control groups, based on the ANCOVA model. The one-sided p-value will be provided for the primary null hypothesis.

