### 2.5.3 Handling of intercurrent events

The primary efficacy analysis will account for different intercurrent events as explained in the following:

- **Discontinuation of study treatment:** Retrieved drop out (RDO) data collected after discontinuation from study treatment will be used for the analysis (treatment policy). Missing data after discontinuation from study treatment will be multiply imputed based on RDO data within each treatment group, and when there are no sufficient RDO data, a control-based Pattern-Mixture Model (PMM) will be used for multiple imputation. In the PMM, missing not at random (MNAR) assumption will be used for inclisiran group. The detailed information is specified in [Appendix 5.4.1.1](#).
- **Use of prohibited LLT:** Use of prohibited LLT (PCSK9 monoclonal antibodies taken before Day 150 visit assessment or other LLT taken within 30 days before Day 150 visit assessment) will be treated in a hypothetical scenario of what would happen had those LLT not been taken, and those participants behaved like other participants in the same treatment group (hypothetical strategy). Data after those intercurrent events will be

excluded for the analysis and will be multiply imputed within each treatment group under MAR assumption.

- **Death:** Death due to CV or non-CV causes is considered as an unfavorable outcome (composite strategy). The LDL-C values at Day 150 after death will be set using the participant's baseline values.

In the case of multiple intercurrent events, death will be the dominant one in the analysis (if present). If a participant experiences only two other intercurrent events and usage of prohibited LLT occurs first, s/he will be handled by the event of usage of LLT (hypothetical strategy). If treatment discontinuation occurs prior to usage of prohibited LLT, then data after usage of LLT will be set missing and s/he will be handled by the event of treatment discontinuation (treatment policy). The detailed imputation model and algorithm are specified in [Appendix 5.4.1.1](#). Number and percentage of participants by each intercurrent event will be summarized by treatment group in core part analyses. Listing will also be provided.

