## **3 Sample size calculation**

This study is designed to randomize approximately 200 Participants (with randomization ratio of 1:1 to inclisiran and placebo arms) in order to provide adequate information to characterize the safety profile of inclisiran as well as to have sufficient power for the primary efficacy endpoint.

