## 5.4 Statistical models

### 5.4.1 Analysis supporting primary objective(s)

#### 5.4.1.1 Primary efficacy analysis

In handling of intercurrent events and missing data not related to intercurrent events, multiple imputation will be used to account for uncertainty in the imputation process and there will be 100 multiply imputed datasets. The results from these 100 imputed datasets will be combined using Rubin's method. Further details are provided below.

For control-based PMM, the missing data after specific intercurrent events in inclisiran group will be imputed using data from control group. The covariates and baseline characteristics which can be predictive of the response will be included in a multiple imputation procedure (SAS PROC MI) and will include the following:

- Baseline value of efficacy measurement (continuous)
- Observed/imputed value of efficacy measurement at Day 30 (continuous)
- Observed/imputed value of efficacy measurement at Day 90 (continuous)
- Observed/imputed value of efficacy measurement at Day 150 (continuous)
- Observed/imputed value of efficacy measurement at Day 180 (continuous)

[figure not shown]
For RDO based imputation model, the missing data after treatment discontinuation will be imputed based on RDO data within each group. The covariates, baseline characteristics and on- or off- treatment status at the same visit with the response which can be predictive of the response will be included in a multiple imputation procedure (SAS PROC MI) and will include the following:

- Baseline value of efficacy measurement (continuous)
- Observed/imputed value of efficacy measurement at Day 30 (continuous)
- Observed/imputed value of efficacy measurement at Day 90 (continuous)
- Observed/imputed value of efficacy measurement at Day 150 (continuous)
- Indicator of on- or off- treatment status at Day 180 (binary)
- Observed/imputed value of efficacy measurement at Day 180 (continuous)

The indicator variable will vary with the imputed response from visit to visit.

1. For those participants who experienced the intercurrent event of using prohibited LLT, set the LDL-C values on or after the usage of LLT missing (out\_step1).

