2. Missing data will be imputed under MAR assumption in this step. The same imputation model as specified for control-based PMM will be used except that the missing data will be multiply imputed using data within each treatment group. SAS PROC MI will be utilized using the FCS REG statement, where only previous measurements will be included for each imputed variable. A total of 100 datasets (out\_step2) will be created. These fully imputed datasets will be utilized in step 3.

3. For participants handled by intercurrent events of treatment discontinuation, if the measurement is missing in (out\_step1) and after treatment discontinuation, set this value back to missing (out\_step3). These datasets (out\_step3) will be utilized in step 4.
4. If there are enough RDO data, the RDO based imputation model will be used in this step. SAS PROC MI will be utilized using the FCS REG statement, where previous measurements and an indicator of on- or off-treatment status at the same visit with the response will be included for each imputed variable. This imputation will be implemented based on data within each group. If there are not enough RDO data, the control-based PMM will be used in this step. With this imputation model, the missing value in the inclisiran group will not be constructed from the observed data in the inclisiran group but rather from the observed and imputed data in the control group. SAS PROC MI will be utilized using the FCS REG statement, where only previous measurements will be included for each imputed variable. The MNAR statement in SAS PROC MI will also be used under MNAR assumption for inclisiran group. After this step, the 100 datasets(out\_step4) will be fully imputed. These datasets will be utilized in step 5. (Which model will be used in this step will be determined before Core Part database lock)
5. For participants who died, set the values after death using his/hers baseline value. (out\_step5)
6. Datasets (out\_step5) will be used in this step. The absolute change and the percentage change values will be calculated in each of the imputed datasets.
7. These 100 datasets will be analyzed using the ANCOVA model for the LDL-C endpoints.
8. The results from the 100 datasets will be combined using Rubin's method via SAS PROC MIANALYZE procedure.

#### 5.4.1.2 Supplementary analysis under estimand 1

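### The RDO imputation model for the primary endpoint can count imputed values of LLT-then-stopped and stopped-then-died participants as off-treatment data: wrong as written, minor in size

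*SAP*

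**What the plan says.** SAP 2.5.3 handles discontinuation of study treatment by treatment policy. Values collected after stopping are the RDO data and are used as they stand. For the rest, "Missing data after discontinuation from study treatment will be multiply imputed based on RDO data within each treatment group", with a control-based pattern-mixture model (PMM) as fallback if RDO data are too few. Use of prohibited LLT is hypothetical (MAR within arm), and death is composite (baseline value).

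Where events coincide, death dominates. Otherwise: "If a participant experiences only two other intercurrent events and usage of prohibited LLT occurs first, s/he will be handled by the event of usage" (LLT use). Only when stopping comes before LLT use is the participant handled as a discontinuation.

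Appendix 5.4.1.1 puts this into steps:

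- Step 1 blanks LDL-C from LLT use onwards.
- Step 2 fills all gaps under MAR within arm, with no term for treatment status.
- Step 3 reopens some of them: "For participants handled by intercurrent events of treatment discontinuation, if the measurement is missing in (out\_step1) and after treatment discontinuation, set this value back to" (that is, blank).
- Step 4, in the RDO branch, runs a regression within each arm, "where previous measurements and an indicator of on- or off-treatment status at the same visit with the response will be included for each imputed variable".
- Step 5 sets values after death to baseline.

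Appendix 5.4.2 reuses the procedure for the other Day 150 endpoints and repeats the same steps for Day 330.

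**The concern.** Step 3 reopens only participants handled as discontinuations. Two kinds of participant who have stopped study treatment are handled as something else: those who used LLT first, and those who stopped and later died. Their step-2 values are still in place when step 4 is fitted, and the imputation procedure cannot tell them from measurements.

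In the inclisiran arm, step-2 values are drawn from a group that is mostly on drug. If the indicator follows actual treatment status, these draws help to estimate the off-treatment term. Section 2.5.3 says that term rests on RDO data. The result is that inclisiran drop-outs can be imputed as better controlled than the retrieved data show. This falls on the part of the estimand meant to carry the consequences of stopping. The only planned sensitivity analysis (SAP 2.5.5) concerns the hypothetical strategy for LLT use and does not test it.

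**Working it through.** **Tracing the steps (RDO branch, inclisiran arm, values after stopping)**

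| Participant | Handled as (2.5.3) | After step 2 | After step 3 | In the step-4 fit |
|---|---|---|---|---|
| Stopped, measured | discontinuation | observed | observed | off-treatment, collected |
| Stopped, not measured | discontinuation | MAR fill | missing | to be imputed |
| LLT, then stopped | LLT | MAR fill | MAR fill | off-treatment if coded by status, not collected |
| Stopped, then died (value missing) | death | MAR fill | MAR fill | off-treatment if coded by status, not collected |
| Died on treatment | death | MAR fill | MAR fill | coding undefined |

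Deaths receive the baseline value only in step 5, after the fit. Nothing in step 4 excludes imputed values.

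**Inputs.** From the SAP: about 200 randomised 1:1, so about 100 per arm; 100 imputations; success if the null hypothesis "is rejected at the one-sided significance level of 0.025". The SAP gives no figure for this point. Its sample size cannot be reproduced either, because no effect, SD, power value or drop-out rate accompanies the statement that the trial is designed "as well as to have sufficient power for the primary efficacy endpoint". Everything below is therefore assumed and shown as a range:

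- k = observed RDO values
- c = step-2 values flagged off-treatment
- d = drop-outs whose Day 150 value is imputed
- g = on/off gap in percentage change, in points

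**Formula.** With few off-treatment records, the off-treatment level is roughly the average of k true and c on-drug-like values:

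- pull on each imputed drop-out = c/(k+c) × g
- shift of the arm mean = (d/100) × pull

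Example: k=5, c=2, d=5, g=30 gives 2/7 × 30 = 8.6 points, and 5/100 × 8.6 = 0.43 points on the arm mean.

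**Simulation.** Steps 2 and 4 were run for 100 inclisiran participants with an on-treatment Day 150 mean of about −52%. The procedure as written was compared with a step-4 fit that leaves out the c participants. Columns 6 and 7 are the mean imputed percentage change in drop-outs.

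| g | k | c | d | Formula pull | As written | c left out | Simulated pull | Arm-mean shift |
|---|---|---|---|---|---|---|---|---|
| 30 | 10 | 1 | 3 | 2.7 | −24.75 | −22.48 | 2.27 | 0.07 |
| 30 | 5 | 1 | 3 | 5.0 | −26.65 | −21.70 | 4.95 | 0.15 |
| 30 | 5 | 2 | 5 | 8.6 | −29.60 | −21.58 | 8.02 | 0.40 |
| 30 | 3 | 3 | 5 | 15.0 | −35.92 | −21.26 | 14.66 | 0.74 |
| 10 | 10 | 1 | 3 | 0.9 | −42.53 | −41.72 | 0.81 | 0.03 |
| 10 | 5 | 1 | 3 | 1.7 | −43.40 | −41.85 | 1.55 | 0.04 |
| 10 | 5 | 2 | 5 | 2.9 | −44.77 | −41.96 | 2.81 | 0.14 |
| 10 | 3 | 3 | 5 | 5.0 | −47.08 | −42.13 | 4.95 | 0.25 |

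At g=0 the two fits differ by less than 0.3 points in drop-outs and by no more than 0.01 on the arm mean. The formula passes 1 point on the arm mean only at more extreme inputs. For example, k=c=5, d=10, g=30 gives 10/100 × 5/10 × 30 = 1.5.

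**Scale.** With 100 per arm and one-sided 0.025, the difference detectable with 90% power is SD × √(2/100) × (1.96 + 1.28). This is 6.9 points for an assumed SD of 15 and 18.3 for an SD of 40. Protocol 2.2 cites placebo-adjusted reductions of 47.9% to 52.3% at Day 510 in earlier phase 3 trials.

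**The case against.** The SAP never defines the indicator for participants handled by LLT use or by death. An LLT-handled participant is imputed as if behaving like the rest of the arm, so coding that person as on treatment is compatible with the text and would remove the problem. That is fair, and it is why the point is conditional. But a status taken from the discontinuation date is the natural coding, and under it the written steps contradict 2.5.3.

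The affected group is also likely to be small. Lipid results are blinded, entry requires no plan to start other LLT, and Protocol 2.3 expects new ASCVD events to be very rare. With only 3 RDO values, the condition of enough RDO data may fail and the PMM would apply. The gap itself may be small. Core doses fall on Day 1 and Day 90, so someone who stops after the second has received all the drug relevant to Day 150. Protocol 4.3 describes LDL-C change at Day 180 after a single dose. All of this limits the size. It does not make the steps right.

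Three stronger readings are not supported:

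- A reader might infer that every PCSK9 antibody user is affected, because Protocol Table 6-4 requires study treatment to be discontinued. Those who stopped study treatment before taking the antibody are handled as discontinuations and are reset in step 3. For statins, ezetimibe and similar drugs, Table 6-4 does not call for discontinuing study treatment.
- A reader might infer that all deaths contaminate the fit. For a death on treatment this depends on a coding the SAP does not give.
- A reader might infer a certain bias towards inclisiran. The direction requires off-treatment LDL-C to be worse than on-treatment, and the documents give no off-treatment figure.

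**Conclusion.** Wrong as written, minor in size. In the RDO branch, step 4 of SAP 5.4.1.1 is fitted to step-2 values of LLT-then-stopped and stopped-then-died participants. If the indicator follows treatment status, those uncollected values act as off-treatment data, against the rule in 2.5.3.

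Given an on/off gap of 10 to 30 points, simulated inclisiran drop-out imputations move towards benefit by about 0.8 to 15 points, and the arm mean by 0.03 to 0.74 points. Counts and gaps are assumptions. The effect vanishes if there is no such participant, if the gap is zero, or under the control-based PMM. Against the detectable differences and expected effect above, it is very unlikely to change the primary conclusion; a reader should not infer that the superiority claim is at risk. The case for correcting it is that the algorithm should do what the text says, and the same steps feed the secondary endpoints and the single-arm Day 330 estimate.

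**What to change.** In step 4 of SAP 5.4.1.1, and in the matching step of 5.4.2 for Day 330, add for the RDO branch:

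1. Before fitting, set to missing or exclude the step-2 values of LLT-handled and deceased participants that fall after they stopped treatment or after death.
2. After the fit, restore the step-2 values for LLT-handled participants, whose strategy is hypothetical, and apply step 5 for deaths.
3. Define the indicator so that only collected values count as off-treatment records, and state its coding for deaths on treatment.

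The cost is a short addition to each appendix section and one data step, with no new data. The SAP history places the current amendment before the final database lock. If the core part is already locked, the corrected fit can be reported as a sensitivity analysis for Day 150 and specified in advance for Day 330.

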#### **2.5.4 Handling of missing values not related to intercurrent event**

Missing values not related to intercurrent event will be multiply imputed within each treatment group under MAR assumption. The detailed imputation model and algorithm are specified in [Appendix 5.4.1.1](#). The primary efficacy analysis will be conducted on each multiply imputed dataset, and the treatment effects estimated from each of those imputed datasets will be combined using Rubin's rule.

#### **2.5.5 Sensitivity analyses**

The following sensitivity analysis will be conducted to assess the robustness of the inferences to various assumptions about the hypothetical strategy for handling usage of prohibited LLT.

- **Tipping point analyses:** a tipping point analysis will be performed to search for the tipping point that reverses the study conclusion. In the tipping point analysis, scale-adjustment to the MAR assumptions will be applied multiplicatively to the imputed values, where the multiplicative factor is allowed to vary for inclisiran group only.

#### **2.5.6 Supplementary analyses**

A plot displaying descriptive mean percentage change in LDL-C from baseline up to Day 180 visit for both treatment groups will be provided, using the observed data.

Subgroup analyses to assess the homogeneity of the treatment effect across demographic and baseline characteristics will be performed in subgroups as specified in [Section 2.2.1](#). The subgroup analyses will use the same ANCOVA model as specified above. The difference in the adjusted means between treatment groups, corresponding two-sided 95% CI and one-sided p-value will also be provided for each of the subgroups. The adjusted means in both treatment groups, corresponding two-sided 95% CI will also be provided for each of the subgroups. The subgroup analysis results will be left blank if the subgroup analysis model did not converge. Forest plot will be provided for subgroup analyses. The multiply imputed datasets created from primary analysis will be used in the subgroup analyses. The results from the subgroup analysis models will be combined using the Rubin's rule.

Two sets of supplementary analyses under different estimand will also be conducted.

For the first one, all three intercurrent events, including discontinuation of study treatment, use of prohibited LLT under certain conditions and death due to CV or non-CV causes, will be handled with a hypothetical strategy. Data after all these intercurrent events will be multiply imputed under missing at random assumption. Missing values not related to intercurrent events will also be multiply imputed under missing at random assumption. Details are specified in [Appendix 5.4.1.2](#).

For the second one, the intercurrent events of discontinuation of study treatment and death due to CV or non-CV causes will be handled in the same way as in the primary analysis. Use of prohibited LLT under certain conditions will be treated with a treatment policy strategy, keeping treatment labels as assigned at randomization. Retrieved drop out (RDO) data collected after use of prohibited LLT under certain conditions will be used for the analysis. Missing data after usage of prohibited LLT will be multiply imputed using a control-based PMM. Missing values not related to intercurrent events will also be multiply imputed using a control-based PMM. Details are specified in [Appendix 5.4.1.3](#).

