9.3.7 Supplementary analysis

Two sets of supplementary analyses will be conducted.

For the first one, all three intercurrent events, including discontinuation of study treatment, use of prohibited LLT under certain conditions and death due to CV or non-CV causes, will be handled with a hypothetical strategy. Data after all these intercurrent events will be multiply imputed under missing at random assumption. Missing values not related to intercurrent events will also be multiply imputed under missing at random assumption.

For the second one, the intercurrent events of discontinuation of study treatment and death due to CV or non-CV causes will be handled in the same way as in the primary analysis. Use of prohibited LLT under certain conditions will be treated with a treatment policy strategy, keeping treatment labels as assigned at randomization. Retrieved drop out (RDO) data collected after use of prohibited LLT under certain conditions will be used for the analysis. If no RDO data was collected, missing data will be multiply imputed using a control-based PMM. Missing values not related to intercurrent events will also be multiply imputed using a control-based PMM.

Details of supplementary analyses will be described in the SAP.

Subgroup analyses

Subgroup analyses to assess the homogeneity of the treatment effect across demographic and baseline characteristics may be performed. All subgroup analyses will be defined in the SAP prior to database lock.

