## 2.6.6 Supplementary analyses

The same subgroup analyses as specified in [Section 2.5.6](#) will be performed for absolute change in LDL-C at Day 150 and percentage change in PCSK9, TC, non-HDL-C and ApoB at Day 150. The difference in the adjusted means between treatment groups, corresponding two-sided 95% CI and two-sided p-value will be provided for each of the subgroups. The adjusted means in both treatment groups, corresponding two-sided 95% CI will also be provided for each of the subgroups.

A plot displaying descriptive mean percentage change in LDL-C from baseline up to Day 360 visit for both treatment groups will be provided, using the observed data.

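### The subgroup analyses aim to assess homogeneity of the treatment effect, but they test each subgroup only against zero and prespecify no between-subgroup difference with a confidence interval

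*SAP*

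**What the plan says.** **Aim.** Protocol 9.3.7 makes the analyses optional and leaves their definition to the SAP: "Subgroup analyses to assess the homogeneity of the treatment effect across demographic and baseline characteristics may be performed". SAP 2.5.6 keeps the aim and commits to the analyses: "Subgroup analyses to assess the homogeneity of the treatment effect across demographic and baseline characteristics will be performed".

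**Model.** SAP 2.5.6: "The subgroup analyses will use the same ANCOVA model as specified above". In that model, set out in SAP 2.5.2, "treatment will be included as fixed-effect factor and baseline LDL-C will be included as a covariate". There is no subgroup term and no treatment-by-subgroup term.

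**Output.** SAP 2.5.6: "The difference in the adjusted means between treatment groups, corresponding two-sided 95% CI and one-sided p-value will also be provided for each of the subgroups". Adjusted means with CIs are also given for both arms. On display: "Forest plot will be provided for subgroup analyses". The analyses reuse the imputed datasets from the primary analysis and pool by Rubin's rule.

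**Secondary endpoints.** SAP 2.6.6 begins "The same subgroup analyses as specified in" 2.5.6. It covers five endpoints (absolute change in LDL-C; percentage change in PCSK9, TC, non-HDL-C and ApoB), with two-sided p-values.

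No visible part of either document plans an interaction estimate, a contrast between subgroups or a heterogeneity test. SAP 2.2.1, which lists the subgroups, is redacted.

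**The concern.** Whether an effect is the same across subgroups is a question about the difference between two treatment effects. The planned p-value answers another question: whether the effect in one subgroup differs from zero. When the overall effect is large compared with its standard error, that p-value is tiny in every subgroup, whether or not the effects differ. A column of very small p-values under a stated aim of homogeneity invites the reader to conclude that homogeneity was tested and supported.

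What is at stake is the claim of consistent efficacy across demographic and baseline groups. If someone later asks whether two subgroups differ, the contrast will have to be built after the results are known.

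**Working it through.** **Inputs from the documents**
- About 200 randomized 1:1 (SAP 3), unstratified (SAP 1.1), so balance within subgroups is expected but not guaranteed.
- One-sided 0.025 for the primary test (SAP 2.5.2).
- Earlier placebo-adjusted LDL-C reductions of 47.9% to 52.3% at Day 510 and 57.2% at Day 330, in other populations (Protocol 2.2).
- 100 imputed datasets (SAP Appendix 5.4.1.1).

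**Assumptions.** The visible text gives no SD, effect size, power figure or subgroup sizes, so the sample size of 200 cannot be reproduced, and no figure is stated for the subgroup analyses. I assume an SD of percentage change of 15 to 35 points, and vary the subgroup split and the true effects.

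**Step 1: what the planned test detects.** With n per arm, power = Φ(δ / (SD·√(2/n)) − 1.96). At δ = 47.9:
- n = 10, SD 20: 47.9/8.94 = 5.36, power 99.97%.
- n = 10, SD 30: 47.9/13.42 = 3.57, power 94.6%.
- n = 25, SD 30: 99.99%.
- n = 5: 96.6% (SD 20) or 71.4% (SD 30).

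Only a very small subgroup with a large SD is likely to miss significance.

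**Step 2: can that test tell equal effects from unequal ones?** I simulated 1,000 complete-data trials per scenario (N = 200, two equal subgroups, SD 25).

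| True effects | Both subgroups significant | Interaction term rejects | Contrast of the two separate estimates rejects |
|---|---|---|---|
| −50 and −50 | 100% | 4.8% | 5.1% |
| −40 and −55 | 100% | 54.8% | 54.7% |

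The planned p-values are the same in both rows. The interaction term separates them, and so does a contrast built from the separate estimates and their standard errors.

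**Step 3: reading the forest plot by eye.** Take SD 20, 50 per arm in each subgroup, and estimates of −60 and −45. The within-subgroup SE is 20·√(2/50) = 4.0, so z is 15 and 11. The 95% CIs are −67.8 to −52.2 and −52.8 to −37.2. They overlap by about 0.7 points, which a reader may take as consistent. The difference is 15 with SE 20·√(4/50) = 5.66, so z = 2.65 and two-sided p is about 0.008.

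**Step 4: precision of an interaction estimate.** SE = SD·√(2/nA + 2/nB), with nA and nB per arm. The difference detectable with 80% power at two-sided 0.05 is (1.96 + 0.84)·SE.

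| SD | SE, 50/50 split | Detectable, 50/50 | Detectable, 10/90 |
|---|---|---|---|
| 15 | 4.2 | 11.9 | 19.8 |
| 20 | 5.7 | 15.8 | 26.4 |
| 25 | 7.1 | 19.8 | 33.0 |
| 30 | 8.5 | 23.8 | 39.6 |
| 35 | 9.9 | 27.7 | 46.2 |

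A true 15-point difference at 50/50 would be detected with 94%, 76% or 56% power at SD 15, 20 or 25. The whole spread of the earlier results is 57.2 − 47.9 = 9.3 points. At SD 20 and 50/50 that gives 9.3/5.66 = 1.64 and power of Φ(1.64 − 1.96), about 38%.

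**The case against.** A reader might infer that the plan cannot assess homogeneity at all, or that its output will look homogeneous whatever the truth. The documents support neither reading. SAP 2.5.6 also plans each subgroup's adjusted difference with a 95% CI, and a forest plot. In Step 2, a contrast built from those separate estimates performs as well as the interaction term. In Step 3, each CI excludes the other subgroup's estimate, so the plot would show the difference to a careful reader. Only the p-values are uninformative.

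Three further points have weight:
- The analysis is supplementary, optional in the protocol and outside the success criterion. A descriptive subgroup display is a legitimate choice in a trial of this size.
- An interaction test here is imprecise, and a non-significant result could be misread as proof of homogeneity.
- SAP 2.2.1 is redacted, so a relevant statement there cannot be fully excluded. However, the readable text of 2.5.6 refers to 2.2.1 only for the subgroups and names the model and outputs itself.

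What remains is that the difference between subgroups, with its CI, is left for the reader to derive, while the one test supplied answers a different question.

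**Conclusion.** The point holds as a gap between the stated aim and the planned inference. The visible text plans estimates and CIs that describe consistency, plus p-values that do not test it, and it does not prespecify the between-subgroup difference. With effects of the size seen earlier, the within-subgroup p-values will be significant in almost any subgroup (94.6% or more at 10 per arm for SD 20 to 30).

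The sizes rest on the assumed SDs, splits and true effects. That the planned test does not compare subgroups rests only on the stated model and outputs. The primary test and the success criterion are unaffected, so this is a worthwhile, low-cost improvement and not a threat to the trial's conclusion.

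**What to change.** In SAP 2.5.6, for each subgroup factor:

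1. Add one ANCOVA on the FAS with treatment, factor, treatment-by-factor and baseline value, fitted to the existing 100 imputed datasets. Report the interaction estimate, 95% CI and nominal p-value, pooled by Rubin's rule.
2. Keep the forest plot and per-subgroup CIs. Label the within-subgroup p-values descriptive, or drop them.
3. State that interaction power is limited and that a non-significant interaction is not evidence of homogeneity.
4. Note that no subgroup factor appears among the visible imputation covariates in Appendix 5.4.1.1 (part of that page is not shown). If much is imputed, this could pull subgroup effects together, so report the proportion imputed by subgroup beside the interaction.

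Apply the same in SAP 2.6.6.

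The cost is a few sentences in the SAP and one extra model per factor and endpoint, with no new data. The document history places SAP Amendment 2 before the final database lock. If the core part has already been locked and analyzed, label the interaction results as added afterwards.
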